6.4.6 Radiation Modification Table

| TOXICITY | MODIFICATION |
|--------------------------------------------------|---------------------------------------------------------------|
| Hematological | |
| Grade 1 or 2 | Continue radiation |
| Grade 3 | Hold radiation until \leq grade 2, then continue |
| Grade 4 | Hold radiation 1 week and until \leq grade 2, then continue |
| Gastrointestinal (nausea, vomiting and diarrhea) | |
| Grade 1 or 2 | Continue radiation |
| Grade 3 | Hold radiation until \leq grade 2, then continue |
| Grade 4 | Discontinue radiation |
| Hepatic dysfunction | |
| Grade 1 or 2 AST or ALT | Continue radiation |
| Grade 3 AST or ALT | Hold radiation until \leq grade 2, then continue |
| Grade 4 AST or ALT | Hold radiation 1 week and until \leq grade 2, then continue |
| Bilirubin ≤ 3.0 mg/dL | Continue radiation |
| Bilirubin > 3.0 mg/dL | Hold radiation until improved ≤ 3.0 , then continue |

| | |
|-------------------------|----------------------------------------------------|
| Child-Pugh score >7 | Hold radiation until improves to CP score ≤ 7 |
| Other non-hematological | |
| Grade 1 or 2 | Continue radiation |
| Grade 3 | Hold radiation until \leq grade 2, then continue |
| Grade 4 | Discontinue radiation |

6.5 Checkpoint Inhibitor: Avelumab

Avelumab will be started 14 days (or 14-18 days) upon completion of SBRT.

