6.3.3 TACE Toxicity Assessment During Therapy

Patient should be seen at least once after TACE before initiation of SBRT. SBRT can be commenced if there is no grade 3 or 4 toxicity, bilirubin ≤ 3.0 mg/dL, Child Pugh score ≤ 7 and the treating physician recommends continuation. Otherwise, a delay in SBRT should occur until toxicities resolve.

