6.4.4 Radiation Therapy Adverse Events

The criteria used for the grading of toxicities encountered in this study are Common Toxicity Criteria (CTC) version 4.0.

Very likely (80-90%)

- Fatigue
- Skin irritation, itchiness, discomfort
- Transient changes in blood work (decrease in blood counts, increase in liver enzymes), without symptoms

Less likely (<30%)

- Nausea, vomiting

- Gastric, esophagus, small bowel or large bowel irritation/ulceration, bleeding, fistula, obstruction or changes in motility following therapy (may require medications or surgery) (<10% permanent changes)
- Chest wall pain, rib fracture (<10%)

Less likely, but serious (<20%)

- Radiation-induced liver disease (RILD) (<5%). Classic RILD is a clinical diagnosis of anicteric ascites, hepatomegaly and elevation of alkaline phosphatase relative to other transaminases that may occur 2 weeks to 3 months following radiation to the liver.
- Non-classic RILD includes elevation of liver enzymes and/or any decline in liver function within 12 weeks from start of therapy (~20%). RILD can lead to liver failure that could lead to death.
- Permanent thrombocytopenia (<1%); this may lead to bleeding
- Kidney injury (<1%); this may lead to changes on imaging

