6.4.5 Radiotherapy Toxicity Assessment During Therapy

Patients will be assessed at least once during radiation therapy for toxicity. Radiation therapy will continue as planned as long as there is no grade 3 or 4 toxicity, bilirubin ≤ 3.0 mg/dL, Child Pugh score ≤ 7 and the treating physician recommends continuation. Otherwise, a delay in radiation therapy should occur with possible continuation of radiation after toxicities resolve. If the patient discontinues radiation therapy prematurely, the patient may be considered for study Avelumab, if the Child score is Child Pugh ≤ 7 and the treating physician recommends protocol treatment continuation.

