6.5.5 Dose Modifications for Avelumab as Single Agent

For avelumab, no dose reductions are permitted in this study, but doses may be omitted based on persisting toxicity. Any adverse event suspected to be immune related should be managed according to the guidance for management of irAEs (see the following tables).

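### Section 6.5 starts avelumab 14-18 days after completed SBRT on timing alone, although Child-Pugh 7 or less is required before SBRT, during SBRT and before avelumab in early stoppers

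*Protocol*

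**What the plan says.** For a patient who finishes SBRT, section 6.5 gives one instruction on the first dose: "Avelumab will be started 14 days (or 14-18 days) upon completion of SBRT". Section 6.5.3 adds a window of 3 days either side of each scheduled dose, for administrative reasons only.

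The steps on either side carry clinical conditions:

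- **Before SBRT (6.3.3):** "SBRT can be commenced if there is no grade 3 or 4 toxicity, bilirubin ≤ 3.0 mg/dL, Child Pugh score ≤ 7", with the treating physician's agreement; otherwise SBRT is delayed.
- **During SBRT (6.4.5):** the same limits apply. The table in 6.4.6 adds, for a score above 7, "Hold radiation until improves to CP score" of 7 or less.
- **Avelumab after SBRT is stopped early (6.4.5):** "the patient may be considered for study Avelumab, if the Child score is Child Pugh ≤ 7", again with the physician's recommendation.

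On avelumab dosing in general, 6.5.5 says that "doses may be omitted based on persisting toxicity".

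Section 6.4.4 describes the liver risk in this period. "Classic RILD is a clinical diagnosis of anicteric ascites, hepatomegaly and elevation of alkaline phosphatase relative to other transaminases", and it "may occur 2 weeks to 3 months following radiation to the liver". It adds: "Non-classic RILD includes elevation of liver enzymes and/or any decline in liver function within 12 weeks from start of therapy", at a rate of about 20%.

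**The concern.** Completing SBRT and then starting avelumab is the ordinary path through the trial, and it is the only transition without a written liver-function condition. Completers did meet the SBRT limits, but those limits bind only up to the last fraction, at least 14 days before avelumab, and 6.4.5 requires only one assessment during the course. Read literally, an early stopper at Child-Pugh 8 may not start avelumab, while a completer at the same score has no stated bar.

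The stake is patient safety. The first dose of a drug with known hepatic toxicity is timed to the opening of the period in which the protocol expects classic RILD. Entry is allowed up to B7 (3.1, criterion 6), so some patients may begin only one point below the range in question.

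**Working it through.** The plan gives no figure to reproduce. The check asks which liver states are left without a stated bar to the first dose, and whether the timing matters.

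**1. What each other rule covers for a completer at day 14-18**

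| Section | Content | Effect on the first dose |
|---|---|---|
| 3.1 | Child-Pugh A-B7 at entry | Assessed before TACE and SBRT |
| 6.5.5 | Omission for persisting toxicity | Possible, but discretionary |
| 6.5.6, 6.5.8 | Drug reactions and suspected immune-related events | Concern reactions to avelumab |
| 7.1 | Two-weekly liver and clotting tests | No threshold |
| 7.2 | Poor-liver-function failure criteria | Stated limits; Child-Pugh 8-9 is not failure in itself; meeting every 3 months |
| 7.5 | Unacceptable toxicity, inter-current disease | Possible, but needs judgement |
| 8.3 | Toxicity stopping rule | Acts on the trial, not the patient |

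**2. Which Child-Pugh 8-9 states 7.2 leaves open**

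Assumption: the usual scale of five items scored 1 to 3, with 7.2 treated as if applied at once, which favours the protocol.

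- Combinations summing to 8: 30. Summing to 9: 45. Total 30 + 45 = 75.
- Section 7.2 removes encephalopathy at 2-3 points, prothrombin time at 2-3 points (its limit of 4 sec read as prolongation) and bilirubin at 3 points (50 umol/L / 17.1 = 2.92 mg/dL).
- With encephalopathy and prothrombin time at 1 point each, the remainder, as bilirubin-albumin-ascites, is:
  - score 8: 1-2-3, 1-3-2, 2-1-3, 2-2-2, 2-3-1 (five);
  - score 9: 1-3-3, 2-2-3, 2-3-2 (three).
- That is 5 + 3 = 8. If 3-point ascites is always counted as refractory, and so already a 7.2 failure, 4 remain: 1-3-2, 2-2-2, 2-3-1, 2-3-2.
- Seven of the 8 involve ascites, and 3 of those 7 have bilirubin at 1 point. Ascites without jaundice is part of how 6.4.4 describes classic RILD.

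These are score combinations, not shares of patients. They show that the open band exists and what it looks like, not how often it occurs.

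**3. Timing of the first dose**

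- Shortest course: four gaps of 24 h = 4 days; 4 + 14 = 18 days from SBRT start.
- Longest course without holds: four gaps of 72 h = 12 days, 12 + 18 = 30 days. Using the 15-day course limit instead (14 elapsed days), 14 + 18 = 32 days.
- 12 weeks = 84 days, so the dose lies inside the non-classic RILD period. If that period runs from TACE (SBRT 21-35 days later, section 6.4), the dose falls at 21 + 18 = 39 to 35 + 32 = 67 days, still inside.
- Classic RILD may begin 2 weeks after radiation, which is the day the dose is scheduled.

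**4. How many patients**

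- At the listed rate of about 20%: 0.20 x 29 = 5.8 and 0.20 x 33 = 6.6 patients with non-classic RILD. This category includes enzyme rises that need not move the Child-Pugh score, and the protocol does not say how many appear by day 14-18.
- Against that, section 1.2 reports no RILD in 73 patients given TACE then SBRT: 0/73, exact two-sided 95% upper limit 1 - 0.025^(1/73) = 4.9%. It does not say whether non-classic RILD was counted.

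Neither figure measures the group of interest, so no count of affected patients can be given.

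**The case against.** The strongest reply is that this is an omission with several safeguards around it. The rules for completers and early stoppers cover different patients. Early stopping can follow grade 4 toxicity (6.4.6), so a written condition there is natural. Section 7.2 already catches the worst decompensation. Sections 6.5.5 and 7.5 are not limited to avelumab toxicity or to later doses, so a physician can hold the first dose for unresolved AST/ALT elevation after SBRT. The two-weekly tests in 7.1 would put the results to hand. No hypothesis, sample size or denominator changes.

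Most of this stands, and it rules out four stronger readings that a reader might infer:

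- **That the protocol contradicts itself.** It does not; the two avelumab start rules apply to different groups.
- **That post-SBRT grade 3-4 AST/ALT is wholly uncovered.** It is covered by discretion, though not by a stated limit.
- **That 6.5.8 makes the plan inconsistent**, because AST/ALT above 5 x ULN ends avelumab there. That table governs events judged immune-related on avelumab, which a rise before the first dose cannot be.
- **That six or seven patients would be dosed unsafely.** The 20% figure does not measure this group, and the 0/73 experience points to a lower frequency of RILD, at least of whatever type was counted.

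What the reply does not answer is Child-Pugh 8-9 short of 7.2. No section makes it a bar for completers, while 6.5 states that the drug will be started and names no clinical reason to wait.

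**Conclusion.** The point holds as a gap in a dosing rule. Followed literally, 6.5 doses a completer at Child-Pugh 8-9 whom the protocol would not irradiate, and whom it would not start on avelumab had SBRT been stopped early. Unresolved grade 3-4 toxicity at that moment is left to judgement. The frequency is unknown and may be low, so this is a worthwhile, inexpensive safety correction and not a threat to the trial's inference.

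The conclusion rests on the usual Child-Pugh scale, on reading the 7.2 prothrombin limit as prolongation, and on the visible text. The treatment-flow figure for section 4 is not shown, so a start condition printed only there cannot be excluded.

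**What to change.** State in 6.5 that the first avelumab dose, for SBRT completers and early stoppers alike, requires all of the following:

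- Child-Pugh score of 7 or less;
- none of the 7.2 poor-liver-function criteria, so bilirubin no higher than 50 umol/L;
- no unresolved grade 3-4 toxicity, including AST/ALT;
- the treating physician's recommendation.

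The bilirubin limit should follow 7.2 and not the 3.0 mg/dL of 6.3.3. Since 3.0 x 17.1 = 51.3 umol/L, the latter would admit a patient whom 7.2 already classes as a treatment failure.

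Check the conditions at the existing two-weekly visit before the dose. If they are not met, delay beyond day 18 until they are, up to a maximum that the sponsor must state (the protocol offers no figure to borrow), then refer the patient to the 7.2 multidisciplinary meeting.

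The cost is a wording amendment and its ethics submission; 7.1 already provides the liver and clotting tests. The analysis population is defined by completion of TACE (8.1), so nobody leaves the denominator. The downside is that some patients will start avelumab later or not at all and still count in the primary rate.

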6.5.1 Avelumab Dosage Form and Packaging

Avelumab is a sterile, clear, and colorless solution intended for IV administration. Avelumab is formulated as a 20 mg/mL solution and will be supplied by the manufacturer in single-use glass vials, stoppered with a rubber septum and sealed with an aluminum polypropylene flip-off seal.

Packaging and labeling will be in accordance with applicable local regulatory requirements and applicable Good Manufacturing Practice (GMP) guidelines. Avelumab will be packed as IMP in boxes each containing 8 vials. The information on the study treatment will be in accordance with approved submission documents.

Avelumab will be shipped in transport cool containers (2°C to 8°C) that is monitored with temperature control devices.

6.5.2 Avelumab Preparation

The contents of the avelumab vials are sterile and non-pyrogenic, and do not contain bacteriostatic preservatives. Any spills that occur should be cleaned up using the facility's standard clean-up procedures for biologic products.

Avelumab must be diluted with 0.9% sodium chloride (normal saline solution). Detailed information on infusion bags and medical devices to be used for the preparation of the dilutions and subsequent administration will be provided. Must use tubing with in line, low protein binding 0.2 micron filter made of polyether sulfone (PES) during administration.

The dose amount required to prepare the avelumab infusion solution will be based on the patient's weight in kilograms (kg). All patients should be weighed within 3 days prior to dosing for each dose to ensure they did not experience either a weight loss or gain of >10% from the weight used for the last dose calculation. For weight change less than 10% the decision to recalculate the avelumab dose can be in accordance with institutional practice. If the patient experienced either a weight loss or gain >10% compared to the weight used for the last dose calculation, the amount of study drug must be recalculated.

Any unused portion of the solution should be discarded in biohazard waste disposal with final disposal by accepted local and national standards of incineration.

6.5.3 Avelumab Administration

Avelumab 10 mg/kg will be administered on Day 1 of each 2-week study cycle. Avelumab may be administered up to 3 days before or after the scheduled day of administration of each cycle due to administrative reasons.

Pre-medication: Avelumab will be administered as a 1-hour IV infusion. In order to mitigate infusion-related reactions, a premedication regimen of diphenhydramine 25 to 50 mg IV or oral equivalent and paracetamol 500 mg IV or oral equivalent is mandatory approximately 30 to 60 minutes prior to each dose of avelumab.

Setting: Avelumab should be administered in a setting that allows for immediate access to an intensive care unit or equivalent environment and administration of therapy for anaphylaxis, such as the ability to implement immediate resuscitation measures. Steroids (dexamethasone 10 mg), epinephrine (1:1,000 dilution), allergy medications (IV antihistamines), bronchodilators, or equivalents, and oxygen should be available for immediate access.

Observation period: Following infusions, patients must be observed for 30 minutes post-infusion for potential infusion-related reactions.

Drug accountability including receipt and return, local discard and destruction, if appropriate, must be completed with appropriate documentation for all study sites. Lot number, and expiry date for Avelumab is recorded in the study site as per local guidelines unless otherwise instructed by the Sponsor.

The investigator is responsible for taking steps to maintain appropriate records and ensure appropriate supply, storage, handling, distribution and usage of study treatments in accordance with the protocol and any applicable laws and regulations.

6.5.4 Avelumab Adverse Event

- Infusion related reaction
- Fatigue
- Immune-related adverse events include pneumonitis, colitis, hepatitis, endocrinopathies including thyroid disorders (hyperthyroidism, hypothyroidism, thyroiditis), adrenal insufficiency, hypophysitis, and diabetes mellitus or hyperglycemia, rash, nephritis and renal dysfunction, encephalitis, eye disorders (including uveitis, iritis), and other immune-mediated reactions including myositis and myocarditis.

6.5.5 Dose Modifications for Avelumab as Single Agent

For avelumab, no dose reductions are permitted in this study, but doses may be omitted based on persisting toxicity. Any adverse event suspected to be immune related should be managed according to the guidance for management of irAEs (see the following tables).

6.5.6 Adverse Drug Reaction Requiring Avelumab Discontinuation or Delays

The following adverse reactions (ADRs) require permanent treatment discontinuation of avelumab:

Any Grade 4 ADRs require avelumab treatment discontinuation except for single laboratory values out of normal range that are unlikely related to trial treatment as assessed by the Investigator(s), do not have any clinical correlate, and resolve within 7 days with adequate medical management.

Any Grade 3 ADRs require avelumab treatment discontinuation except for any of the following:

- Transient (≤ 6 hours) Grade 3 flu-like symptoms or fever, which is controlled with medical management
- Transient (≤ 24 hours) Grade 3 fatigue, local reactions, headache, nausea, or emesis that resolves to Grade ≤ 1
- Single laboratory values out of normal range (excluding Grade ≥ 3 liver function test increase) that are unlikely related to trial treatment according to the Investigator(s), do not have any clinical correlate, and resolve to Grade ≤ 1 within 7 days with adequate medical management
- Tumor flare phenomenon defined as local pain, irritation, or rash localized at sites of known or suspected tumor
- Change in Eastern Cooperative Oncology Group Performance Status (ECOG PS) to 3 that resolve to ≤ 2 within 14 days (infusions should not be given on the following cycle, if the ECOG PS is 3 on the day of trial drug administration).

Any Grade 2 ADR should be managed as follows:

- If a Grade 2 ADR resolves to Grade ≤ 1 within 2 weeks treatment may continue.
- If a Grade 2 ADR does not resolve to Grade ≤ 1 within 2 weeks, avelumab should be held. If after another 2 weeks the event has not resolved to Grade 1, the patient should permanently discontinue treatment with an avelumab (except for hormone insufficiencies, that can be managed by replacement therapy; for these hormone insufficiencies, up to 2 subsequent doses may be omitted).
- Upon the second occurrence of the same Grade 2 ADR (except for hormone insufficiencies that can be managed by replacement therapy) in the same patient, treatment with avelumab has to be permanently discontinued.

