6.5.8 Avelumab: Immune-Related Adverse Events

Because inhibition of PD-L1 stimulates the immune system, avelumab may cause toxicity by increasing the immune response, leading to inflammatory reactions collectively referred to as immune-related adverse events (irAEs).

Immune-related adverse events described with this class of drugs include drugs include dermatitis, pneumonitis, colitis, hepatitis, endocrinopathies including thyroid disorders (hyperthyroidism, hypothyroidism, thyroiditis), adrenal insufficiency, hypophysitis, and diabetes mellitus or hyperglycemia, rash, nephritis and renal dysfunction, encephalitis, eye disorders (including uveitis, iritis), and other immune-mediated reactions including myositis and myocarditis.

Any adverse event which may have an underlying immune-mediated mechanism including those described above, and without other confirmed etiologies, should be considered immune-related and managed according to guidelines described in this section.

Treatment of irAEs is mainly dependent upon severity (NCI CTCAE grade):

- Grades 1 to 2: treat symptomatically or with moderate dose steroids, more frequent monitoring.
- Grades 1 to 2 (persistent): manage similar to high grade AE (Grades 3 to 4).
- Grades 3 to 4: treat with high dose corticosteroids.

For patients receiving avelumab alone, any event suspected to be immune-related should be managed according to the guidance for management of irAEs in this section and Table.

| Gastrointestinal irAEs | | |
|------------------------------------------------------------------------------------------------------------------------------------------------------------------------------------------------------------------------------------------------------------------------------------|----------------------------------------------------------------------------------------------------------------------------------------------------------------------------------------------------------------------------------------------------------|-----------------------------------------------------------------------------------------------------------------------------------------------------------------------------------------------------------------------------------------------------------------------------------------------------------------------------------------------------------------------|
| Severity of Diarrhea/Colitis (NCI-CTCAE v4) | Initial Management | Follow-up Management |

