|------------------------------------------------------------------------------------------------------------------|----------------------------------------------------------------------------------------------------------------------------------------------------------------------------------------------------------------------------------------------------------------------------------------|------------------------------------------------------------------------------------------------------------------------------------------------------------------------------------------------------------------------------------------------------------------------------------|
| | 
Monitor symptoms daily; consider hospitalization
 
1.0 to 2.0 mg/kg/day prednisone or equivalent
 
Add prophylactic antibiotics for opportunistic infections
 
Consider bronchoscopy, lung biopsy
 | 
over at least 1 month, and then resume avelumab therapy following steroids taper
 
If not improving after 2 weeks or worsening:
 
Treat as Grade 3 to 4.
 |
| Grade 3 to 4 Grade 3: Severe new symptoms; New/worsening hypoxia; Grade 4: Life-threatening | 
Permanently discontinue avelumab therapy.
 
Hospitalize.
 
Pulmonary and Infectious Disease consults.
 
1.0 to 2.0 mg/kg/day prednisone or equivalent
 
Add prophylactic antibiotics for opportunistic infections
 
Consider bronchoscopy, lung biopsy
 | 
If improves to Grade ≤ 1:
 
Taper steroids over at least 1 month
 
If not improving after 48 hours or worsening:
 
Add additional immunosuppression (for example, infliximab, cyclophosphamide, IV immunoglobulin, or mycophenolate mofetil)
 |
| Hepatic irAEs | | |
| Grade of Liver Test Elevation (NCI-CTCAE v4) | Initial Management | Follow-up Management |
| Grade 1 Grade 1 AST or ALT $>3.0 \times$ ULN and/or Total bilirubin $>$ ULN to $1.5 \times$ ULN | Continue avelumab therapy | 
Continue liver function monitoring
 
If worsens:
 
Treat as Grade 2 to 3 or 4.
 |
| Grade 2 AST or ALT >3.0 to $5 \times$ ULN and/or Total bilirubin >1.5 to $3 \times$ ULN | 
Withhold avelumab therapy
 
Increase frequency of monitoring to every 3 days.
 | 
If returns to Grade ≤ 1 :
 
Resume routine monitoring; resume avelumab therapy.
 
If elevation persists >5 to 7 days or worsens:
 
Treat as Grade 3 to 4.
 |

| | | |

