|--------------------------------------------------------------------------------------------------------------------------|------------------------------------------------------------------------------------------------------------------------------------------------------------------------------------------------------------------------------------------------------------------------------------------------------------------------------------------------------|------------------------------------------------------------------------------------------------------------------------------------------------------------------------------------------------------------------------------------------------------------------------------------------------------------------------------------------------------|
| 
Grade 3 to 4
 
AST or ALT $>5 \times$ ULN and/or total bilirubin $>3 \times$ ULN
 | 
Permanently discontinue therapy
 
Increase frequency of monitoring to every 1 to 2 days
 
1.0 to 2.0 mg/kg/day prednisone or equivalent
 
Add prophylactic antibiotics for opportunistic infections
 
Consult gastroenterologist/
 
Consider obtaining MRI/CT scan of liver and liver biopsy if clinically warranted
 | 
If returns to Grade ≤ 1:
 
Taper steroids over at least 1 month
 
If does not improve in >3 to 5 days, worsens or rebounds:
 
Add mycophenolate mofetil 1 gram (g) twice daily
 
If no response within an additional 3 to 5 days, consider other immunosuppressants per local guidelines.
 |
| Renal irAEs | | |
| 
Grade of Creatinine Increased
 
(NCI-CTCAE v4)
 | 
Initial Management
 | 
Follow-up Management
 |
| 
Grade 1
 
Creatinine increased $>$ ULN to $1.5 \times$ ULN
 | 
Continue avelumab therapy
 | 
Continue renal function monitoring
 
If worsens:
 
Treat as Grade 2 to 3 or 4.
 |
| 
Grade 2 to 3
 
Creatinine Increased >1.5 and $\leq 6 \times$ ULN
 | 
Withhold avelumab therapy
 
Increase frequency of monitoring to every 3 days
 
1.0 to 2.0 mg/kg/day prednisone or equivalent.
 
Add prophylactic antibiotics for opportunistic infections
 
Consider renal biopsy
 | 
If returns to Grade ≤ 1:
 
Taper steroids over at least 1 month, and resume avelumab therapy following steroids taper.
 
If worsens:
 
Treat as Grade 4.
 |

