7.2 Decision on Resectability, Subsequent Treatment and Treatment Failure

A multidisciplinary meeting consists of surgeons, oncologists, and radiologists will be held every 3 months to evaluate treatment response/failure, to decide on subsequent treatment.

Successful downstage and disease control (as defined by complete response, partial response and stable disease) will be evaluated for resection or transplantation of HCC

UCSF Criteria will be used to determine the suitability of transplantation

- Single tumor $\leq 6.5\text{cm}$
- Or up to 3 tumors $\leq 4.5\text{cm}$, and total sum is 8cm
- No vascular invasion

Treatment failure can be due to either poor liver function or tumor progression

Poor liver function is defined as

- Hepatic encephalopathy,
- Diuretic refractory ascites,
- Variceal bleeding,
- Bilirubin $>50\text{umol/L}$,
- Prothrombin time $>4\text{sec}$, or
- Child Pugh C status.

Tumor progression is defined as

- Extra-hepatic disease,
- New onset major vascular invasion (portal vein or hepatic vein invasion),
- Progressive disease according to mRECIST,

In patients who have treatment failure, unacceptable toxicity, or they have reached the end of treatment. Subsequent treatment will be decided in multidisciplinary panel based on best interests of patients. There is no restriction on choice of subsequent treatment.

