7.7.6 Methods of Recording Adverse Events

All AEs must be documented in the appropriate section of the CRF. An SAE report form (initial or follow up) must be completed in addition.

The following aspects must be recorded for each event in the CRF:

A description of the AE in medical terms, not as reported by the subject;

- The date of onset (start date)
- The time of onset (start time)
- The date of recovery (stop date)
- The time of recovery (stop time)
- The severity of the sign and/or symptom or clinically significant abnormal laboratory value according to NCI-CTC, Version 4.0. If no toxicity grade is described for a given sign, symptom or abnormal laboratory value, the Investigator(s) will grade the severity as mid (grade 1), moderate (grade 2), severe (grade 3), or life-threatening or disabling (grade 4).

- Death (grade 5) as defined by NCI-CTCAE v.4.0 is mainly regarded as an outcome and will be documented accordingly (see below).
- The causal relationship to Avelumab, TACE and radiotherapy as assessed by the Investigator(s); the decisive factor in the documentation is the temporal relation between the AE and the study drug. The following judgments of the causality to study drug or study procedures are to be used:
 - Not Related = not suspected to be reasonably related to the investigational product. AE could not medically (pharmacologically/ clinically) be attributed to the investigational product under study in this protocol
 - Related = suspected to be reasonably related to the investigational product. AE could medically (pharmacologically/ clinically) be attributed to the investigational product under study in this protocol
- Action taken on Avelumab (none, medication discontinued, dose reduction, medication delayed, reduction of infusion rate).
- Other action (none, concomitant medication given, new or prolonged hospitalization, procedural surgery).
- The outcome according to the following definitions:
 - Recovered without sequelae (AE disappeared)
 - Recovered with sequelae (AE has resulted in permanent disability/incapacity)
 - Not yet recovered
 - Not recovered at death
 - Change in toxicity grade/severity or seriousness (e.g., an AE with no change of toxicity grade but newly classified as an SAE due to hospitalization)
 - Fatal (AE resulted in death)
- Concomitant medication given: Yes or No (Note: If this question is answered “Yes” the corresponding serious criteria must be ticked)
 - Subject died
 - Life-threatening

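### Section 6.5.6 bars liver-test rises from the Grade 3 laboratory exception but not from the Grade 4 one, so a rise with a confirmed non-trial cause meets a softer stopping rule at the worse grade

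*Protocol*

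**What the plan says.** Protocol section 6.5.6 lists the adverse drug reactions after which avelumab must be stopped for good. For Grade 4: "Any Grade 4 ADRs require avelumab treatment discontinuation except for single laboratory values out of normal range that are unlikely related to trial treatment". The sentence adds two conditions: no clinical correlate, and resolution within 7 days under medical management.

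Grade 3 reactions also require a permanent stop, with a list of exceptions. The laboratory item in that list reads: "Single laboratory values out of normal range (excluding Grade ≥ 3 liver function test increase) that are unlikely related to trial treatment". It too requires no clinical correlate and recovery within 7 days, here to Grade 1 or lower.

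Section 6.5.8 covers immune-related events. An event that may be immune-mediated, and is "without other confirmed etiologies, should be considered immune-related and managed according to guidelines described in this section". For Grade 3 to 4 liver-test elevation its hepatic table says: "Permanently discontinue therapy".

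**The concern.** A stopping rule should not become easier on the patient's treatment as the toxicity gets worse. Section 6.5.6 does this for liver tests. The restriction that keeps them out of the laboratory exception is written only into the Grade 3 list and does not qualify the separate Grade 4 sentence.

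The threshold in that restriction is Grade 3 or higher. Inside a list that concerns only Grade 3 events, the words for higher grades do nothing unless Grade 4 was also meant to be caught. This points to a misplaced phrase, not a deliberate choice, and the protocol gives no reason for a softer Grade 4 rule.

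At stake is the mandatory character of a safety stop in patients whose livers are already under strain. They may enter with Child-Pugh B7 function and ALT up to 3×ULN (section 3.1), and they receive TACE and SBRT before avelumab.

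**Working it through.** The protocol states no figure on this point. The check compares the two rules and then asks which cases other sections already catch.

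**1. The two laboratory exceptions in section 6.5.6**

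| Condition for escaping the stop | Grade 3 | Grade 4 |
|---|---|---|
| Single out-of-range laboratory value | required | required |
| Judged unlikely to be related to trial treatment | required | required |
| No clinical correlate | required | required |
| Recovery within 7 days | to Grade 1 or lower | resolution, no target grade named |
| Liver-test rises shut out | yes, at Grade 3 and above | no |

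**2. A test case.** Take an isolated ALT rise with a confirmed cause outside the trial treatments, no clinical correlate, and back to normal within 7 days. This meets either recovery wording.

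- At Grade 3 the liver-test restriction closes the exception, so avelumab stops permanently.
- At Grade 4 the exception is open, so no stop is mandated.

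**3. What other sections already catch**

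- *Section 6.5.8.* A possibly immune-mediated rise without another confirmed cause goes to the hepatic table. AST or ALT above 5×ULN, or bilirubin above 3×ULN, stops avelumab permanently at Grade 3 and Grade 4 alike. There is no inversion for these events. A rise with another confirmed cause falls outside this section.
- *TACE or SBRT as the cause.* Section 7.7.6 asks for causality to avelumab, TACE and radiotherapy. A rise caused by TACE or SBRT is therefore arguably related to trial treatment and not exempt. The text is not fully firm, because the same section defines relatedness by the investigational product, which section 6.1 says is avelumab. The finding does not depend on this reading.
- *Section 7.2, bilirubin.* "Treatment failure can be due to either poor liver function or tumor progression", and bilirubin above 50 µmol/L counts as poor liver function. The protocol gives no ULN. Assuming 17, 19 or 21 µmol/L:
  - 3 × 17 = 51 µmol/L
  - 3 × 19 = 57 µmol/L
  - 3 × 21 = 63 µmol/L

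  The Grade 3 to 4 bilirubin threshold exceeds 50 µmol/L in each case. The two limits coincide at a ULN of 50 / 3 = 16.7 µmol/L. Over the assumed range, any Grade 4 bilirubin value already counts as treatment failure. Section 7.2 sets no AST or ALT limit.
- *Sections 7.2 and 7.5, discretion.* After treatment failure, "Subsequent treatment will be decided in multidisciplinary panel based on best interests of patients". Section 7.5 allows removal for unacceptable toxicity or intercurrent disease. Both rest on judgement and do not replace a mandatory stop.

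**4. What is left.** A Grade 4 liver-test rise, mainly AST or ALT, with a confirmed non-trial cause, no clinical correlate, and resolution within 7 days.

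**5. Comparison of the two avelumab rules graded on liver tests.** The hepatic table in 6.5.8 treats Grades 3 and 4 equally. For the remainder in step 4, section 6.5.6 is more lenient at Grade 4.

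**The case against.** The strongest objection is that the remaining case may be empty. Section 6.5.6 governs adverse drug reactions. A rise with a confirmed non-trial cause would be classed as not related under section 7.7.6, so it is not naturally a drug reaction and neither rule would apply. If the other cause is merely likely, section 6.5.8 takes over and stops avelumab at both grades. This does not succeed, because both exceptions in 6.5.6 are written for values judged unlikely to be related. If such values lay outside the section, both exceptions and the liver restriction itself would have no content.

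Second, the conditions are many and few patients will meet them all. That is true and limits the size of the point. The exception also only lifts a mandatory stop; it does not require avelumab to continue.

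Third, the protocol treats Grade 4 liver events as grave elsewhere. Section 7.7.7 requires potential drug-induced liver injury (Hy's Law cases) to be reported as serious, and section 8.3 counts Grade 4 or 5 hepatic events as excessive toxicity. This supports the view that the leniency was unintended, but neither provision stops treatment in an individual patient.

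Fourth, consistency could be restored the other way, by relaxing Grade 3. That is possible, but it runs against the evident intent of the Grade 3-or-higher wording and against the hepatic table in 6.5.8.

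**Conclusion.** The concern holds as a minor drafting error in a safety rule. As written, section 6.5.6 requires permanent discontinuation for an unrelated, isolated, transient liver-test rise at Grade 3 and not for the same kind of rise at Grade 4.

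Its reach is small: mainly AST or ALT, and only with another confirmed cause outside the trial treatments. The protocol does not allow a count of affected patients; few are to be expected among the 33 planned. The conclusion rests on reading the Grade 4 sentence literally and on treating values judged unlikely to be related as within the section, as its own exceptions do. The view that bilirubin is largely covered elsewhere also assumes a ULN of 17 to 21 µmol/L. The primary endpoint, the sample size and the decision rule are not affected.

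**What to change.** In the Grade 4 sentence of section 6.5.6, directly after the mention of single out-of-range laboratory values, insert the parenthesis *(excluding liver function test increase)*. Leave the rest of the sentence as it is.

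For liver tests, Grade 4 is then at least as strict as Grade 3 and agrees with the hepatic table in 6.5.8. The different recovery wording at the two grades no longer matters for liver tests; for other laboratory values it is unchanged.

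The cost is one parenthesis, which can go into the next amendment. A few patients with an unrelated, transient Grade 4 rise would have to stop avelumab, as the protocol already requires at Grade 3.
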